#### 12.1.2. Secondary Objective: Drops Missed

Formal hypothesis: Drop aids will be effective in delivering the proper amount of drops, thereby reducing the number of missed drops for patients.

Testable hypothesis: Differences in drops missed with drop aid device compared to without drop aid device will show efficacy in drop aid device.

Null hypothesis: Patients assigned to a drop aid device will not result in less drops missed when compared to patients who are not assigned to a drop aid device.

Alternate hypothesis: Patients assigned to a drop aid device will result in minimal missed drops when compared to patients who are not assigned to a drop aid device.

### 12.1.3. Secondary Objective: Patient Satisfaction

Formal hypothesis: Drop aid devices will prove greater patient satisfaction than administrations without a drop aid device.

Testable hypothesis: Mean patient satisfaction to those assigned to a drop aid device compared to mean patient satisfaction scores to those not assigned to a drop aid device.

Null hypothesis: Patients assigned to a drop aid device will not show greater patient satisfaction than patients not assigned to a drop aid device.

Alternate hypothesis: Patients assigned to a drop aid device will show greater patient satisfaction than patients not assigned to a drop aid device.

$$H_0: \mu_s < \mu_{sd} - \delta$$

$$H_A: \mu_s \geq \mu_{sd} - \delta$$

Where  $\mu_s$ , is the mean patient satisfaction without the drop aid device,  $\mu_{sd}$  is the mean patient satisfaction with the drop aid device.

### 12.1.4. Secondary Objective: Intention of Long term use

Formal hypothesis: Patients assigned to a drop aid device will claim greater interest in long term use of the drop aid device, than declining long term use of the drop aid device.

Testable hypothesis: Mean patients claiming interest in long term use of the drop aid device compared to mean patient declining interest in long term use of the drop aid device.

Null hypothesis: Patients assigned to a drop aid device will not show greater mean interest in long term use of the drop aid device.

Alternate hypothesis: Patients assigned to a drop aid device will show greater mean interest in long term use of the drop aid device.

$$H_0: \mu_y < \mu_n - \delta$$

$$H_A: \mu_y \geq \mu_n - \delta$$

Where  $\mu_y$ , is the mean patients who claimed interest in long term use of the device,  $\mu_n$  is the mean patient who denied interest in long term use of the device.

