### 5 Study Design

This interventional clinical trial is a prospective, single center, randomized controlled study. Patients being treated for their glaucoma at BMC's Yawkey Eye Clinic will be selected. Patients will be randomly placed, without manipulations by the principle investigator or any member of the research team, on one of the drop aid devices (including Fabrication Autodrop Eye Drop Guide, Simply Touch Eye Drop Applicator, Owen Mumford OP 6100 Autosqueeze), in addition to a no drop aid control, for a total of 4 groups.

Subjects have an equal chance of being randomized to one of the following study arms:

- Arm A: No intervention – Control
- Arm B: Active Comparator- Eye Drop Aids Including:
  - Simply Touch Eye Drop Applicator
  - Fabrication Autodrop Eye Drop Guide
  - Owen Mumford OP 6100 Autosqueeze

The primary endpoint is the comparison of baseline IOP measurement and follow-up IOP measurement. This comparison will determine the efficacy of using a drop aid. The secondary endpoints include the precision of the drop aid, patient satisfaction, and their likelihood to use a drop aid outside of the study. Data collection for assessment of study objectives will be obtained via standard of care clinic visits and completion of study diary and satisfaction survey by the patient with assistance of research team, if needed.

See the Appendix section 15.1 for a schematic of the study design and section 15.3 for drop aid labels and instructions.

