## 12.2 Sample Size Determination

The sample size was determined by the maximum number of subjects which could be randomized given the budgetary constraints of the grant funding. It was determined that a total of ten patients per group was financially feasible, thus a total of 40 patients will be enrolled in this study in approximately 1 year.

Enrolling the projected 40 subjects in 1 year is feasible, as the ophthalmology department sees approximately 275 glaucoma patients weekly. Due to the high volume of the glaucoma clinic, the study team should be able to easily recruit their target. Additionally, the study team is comprised of multiple

investigators and research assistants who have been delegated tasks on this protocol which can provide full-time recruitment coverage.

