### 12.3 Statistical Methods

A variety of statistical analysis will be used to analyze the results. A paired t-test will be the primary method of analysis. Any significant differences measured will be between the pre and post intervention, with the patient serving as their own control. However, the analysis will not be limited to a paired t-test and will also likely include ANOVA, chi-squared, p-value, linear regression, among others. Other outcomes such as length of time until completion of drops will also be measured and compared to no drop aid controls. Significant differences will be measured with similar statistical analysis as stated previously. Satisfaction of use will be measured with a survey and results will be averaged among those in the same cohort. Any significant differences will also be measured with similar statistical analysis stated previously.

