15.2.4 Satisfaction Survey

**Study ID:** \_\_\_\_\_

**Name of study team member completing this form:** \_\_\_\_\_

**Date:** \_\_\_\_\_

**Study Visit:**     3-week phone call         Follow-up clinic visit

1. Do you like the drop aid?
  - a. Yes
  - b. No
  - c. I am not on a drop aid
  - d. I did not use the drop aid
2. Is it easier to instill drops with the help of the drop aid compared without the drop aid?
  - a. Yes
  - b. No
  - c. I am not on a drop aid
  - d. I did not use the drop aid
3. How many times did you miss instilling drops with the help of drop aid?
  - a. None
  - b. 1
  - c. 2
  - d. 3 or more
  - e. I am not on a drop aid
  - f. I did not use the drop aid
4. How many times do you miss instilling drops just using your glaucoma drops?
  - a. None
  - b. 1
  - c. 2
  - d. 3 or more
5. Would you use the drop aid long term?
  - a. Yes
  - b. No
  - c. I am not on a drop aid
  - d. I did not use the drop aid

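### Section 12.1.4 writes one Yes/No proportion as two means; its formula admits a tie at δ = 0 and a minority of Yes for any δ > 0, and no test is assigned

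*Combined protocol and SAP*

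**What the plan says.** Intention to use a drop aid long term is the third secondary outcome in section 4.2.2. Section 12.1.4 gives its hypothesis for device patients only: "Patients assigned to a drop aid device will claim greater interest in long term use of the drop aid device, than declining long term use". The testable form is "Mean patients claiming interest in long term use of the drop aid device compared to mean patient declining interest in long term use". The symbols follow suit: μ_y is a mean for patients who claimed interest, and μ_n "is the mean patient who denied interest in long term use of the device". The formal pair is H_0: μ_y < μ_n − δ against H_A: μ_y ≥ μ_n − δ. δ is given no value, sign or unit. The worded alternative carries no margin and asks for greater interest.

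The data come from item 5 of the satisfaction survey (section 15.2.4): "Would you use the drop aid long term". A patient chooses one of four answers: Yes, No, not on a drop aid, or did not use it. The schedule of events places the survey at the 3-week call and the 6-week visit only.

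Section 12.3 names a paired t-test as the main method and describes it as a before-and-after comparison within the patient. It expects ANOVA, chi-squared and other methods as well, without tying them to outcomes. For the satisfaction survey it adds: "Any significant differences will also be measured with similar statistical analysis stated previously". It states no alpha or sidedness.

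**The concern.** A hypothesis about two means invites a comparison of two groups, but there is only one group and one answer per patient at each survey. Whoever carries out section 12.1.4 has to decide what is being compared, by which test and against which margin, and the text settles none of these.

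Two things are at stake. First, the formula and the words disagree about what counts as success, so the same result could be reported as supporting the hypothesis under one and not under the other. Second, if the Yes and No shares are entered into a two-group test, each patient is counted twice and the evidence looks stronger than it is.

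**Working it through.** **Inputs**

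- Group size and total (section 12.2): "a total of ten patients per group was financially feasible, thus a total of 40 patients will be enrolled in this study". Number of groups (section 5): "in addition to a no drop aid control, for a total of 4 groups". Check: 4 × 10 = 40, as stated.
- Device patients: 3 × 10 = 30. This is derived, not stated. Section 5 also says "Subjects have an equal chance of being randomized to one of the following study arms" and then lists Arm A and Arm B; read as 1:1 between those arms, that would give 20 device patients.
- Alpha and sidedness: not stated. I assume 5% two-sided and also show one-sided results.
- δ: not stated. I show a range.

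**Step 1: what the formula says.** If every device patient answers Yes or No, μ_n = 1 − μ_y. Substituting into μ_y ≥ μ_n − δ gives 2μ_y ≥ 1 − δ, that is, a Yes share ≥ (1 − δ)/2.

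| δ (assumed) | Smallest Yes share that satisfies H_A |
|---|---|
| 0 | 50% (a tie) |
| 0.05 | 47.5% |
| 0.10 | 45% |
| 0.20 | 40% |
| 0.30 | 35% |

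If a share q reports not using the aid and stays in the denominator, the boundary is (1 − q − δ)/2. With q = 0.10 and δ = 0.20 it is 35%.

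**Step 2: variance of the difference.** Let K be the number of Yes answers among n. The difference in shares is K/n − (n − K)/n = 2K/n − 1. With a true Yes share of 0.5:

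- Correct variance: 4 × 0.25/n = 1/n.
- Variance if the shares are treated as two independent groups of n: 2 × 0.25/n = 0.5/n, half the correct value.

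**Step 3: false-positive rate at n = 30**, by exact enumeration of K ~ Binomial(30, 0.5), all answering Yes or No. The tail probabilities are P(K ≥ 19) = 0.1002, P(K ≥ 20) = 0.0494 and P(K ≥ 21) = 0.0214.

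| Analysis | Rejects at | Rate |
|---|---|---|
| Two independent groups, uncorrected z, chi-squared or t, two-sided 5% | ≥ 19 or ≤ 11 Yes | 2 × 0.1002 = 20.0% |
| Same, hypothesised direction only (one-sided 5% or 2.5%) | ≥ 19 Yes | 10.0% |
| Two independent groups, Yates or Fisher, two-sided 5% | ≥ 20 or ≤ 10 Yes | 2 × 0.0494 = 9.9% |
| Exact binomial, two-sided 5% | ≥ 21 or ≤ 9 Yes | 2 × 0.0214 = 4.3% |
| Exact binomial, one-sided 5% | ≥ 20 Yes | 4.9% |

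The large-sample value for the first row is 2(1 − Φ(1.96/√2)) = 16.6%.

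**Step 4: sensitivity of the first row.** The rate moves with n because the counts are discrete: 11.5% at 20, 15.2% at 24, 23.0% at 25, 12.2% at 27, 18.5% at 28 and 13.6% at 29. At n = 30 with 10% or 20% non-use answers kept in the denominator it is 14.9% or 12.6%.

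**Step 5: example.** Take 19 Yes and 11 No. As two groups of 30, z = (8/30)/√(0.5/30) = 0.2667/0.1291 = 2.07, two-sided p = 0.039. The exact binomial test gives one-sided p = 0.10 and two-sided p = 0.20.

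**The case against.** The strongest reply is that the plan prescribes no two-sample test here. The t-test that section 12.3 names is paired, and a chi-squared test could equally be the one-sample kind on the Yes and No counts. Either would be sound: at n = 30 a paired t-test on a Yes-minus-No score rejects at the same counts as the exact binomial test, with a rate of 4.3% two-sided. This stands. A reader might infer from the wording of section 12.1.4 that the planned analysis has a 20% false-positive rate. The documents do not support that. The figure needs an uncorrected two-group test, two-sided 5%, exactly 30 respondents and no non-use answers, and section 12.3 fixes none of these. The alternative is directional, and in that direction the rate is about 10%.

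The paired test does not close the gap, however. Section 12.3 describes it as before against after, and item 5 has no baseline value. A valid analysis would be reached only through a choice the plan does not record.

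On the margin, a reader might infer that the plan accepts a minority of Yes answers as success. That holds only if δ > 0, and δ has no value or sign. The same undefined δ appears in sections 12.1.1 and 12.1.3, so it looks like a shared template and not a deliberate margin. The conflict with the words remains for δ = 0, where a tie satisfies H_A; only a negative δ would remove it.

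Finally, this is the last of three secondary outcomes, taken from a survey item with no control comparison, in a study whose size was set by budget. That limits the consequence but does not make the stated hypothesis correct.

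**Conclusion.** The point holds in this form. Section 12.1.4 states one proportion as two means, and its formula disagrees with its worded alternative for every δ ≥ 0. Neither finding depends on which test is used. Section 12.3 leaves the test, alpha and sidedness open, and the one paired analysis it describes cannot be applied to item 5.

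The inflated error rate is conditional. If the two shares were compared as independent groups, the rate at n = 30 would be about 10% to 20% against a nominal 5%, assuming a true even split and that everyone answers Yes or No. It is a hazard of an unspecified analysis, not a property of the written plan. The correction should be made before analysis, because it is cheap and the present hypothesis is wrong as written.

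**What to change.** Replace the hypothesis in section 12.1.4 with a one-sample statement:

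> Let p be the proportion of patients assigned to a drop aid who answer Yes to survey item 5 at the final study visit. H0: p ≤ 0.5; HA: p > 0.5. The test is the exact binomial test at a one-sided alpha of [state value]. The estimate of p is given with an exact 95% confidence interval, overall and, descriptively, for each device. Patients who answer that they did not use the drop aid are counted as not Yes; a sensitivity analysis excludes them.

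Delete μ_n and δ from this section, and add a line to section 12.3 that assigns this test to this outcome.

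The cost is wording only: no new data, visits or patients. There are two consequences to accept. Borderline splits will look less favourable; 19 Yes and 11 No, for example, would no longer reach one-sided 5%. Counting non-use as not Yes also makes the main analysis stricter than asking whether Yes outnumbers No; the sensitivity analysis answers that narrower question.

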#### 4.2.2 Secondary Outcome Measures

The following secondary outcomes will also be measured:

1. Number of times a patient missed their eye when instilling eye drops
2. Patient satisfaction responses with treatment arms
3. Intention to use a drop aid long term

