## 9.4 Early Termination Visit

The subject can be terminated early from the study if there is a change in eye medication as determined by their SOC provider. Subjects can also be withdrawn from the study if they demonstrate non-compliance for study procedures.

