## 10.4 Stopping Rules

A subject will be withdrawn from the study for any of the following reasons but are not limited to:

- Change to eye drop regimen as determined by their SOC provider

- Failure to comply with drop aid instructions
- SAE or UP resulting from the administered study device

The study will be stopped if the PI, [name], determines that the number of AEs, SAE, and/or UPs exceed that of SOC ocular procedures.

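### The long-term-use outcome in 12.1.4 has only a yes and a no category, so device patients who report non-use, or are withdrawn for non-compliance without a final survey, fall in neither and apparent interest can be inflated

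*Combined protocol and SAP*

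**What the plan says.** Section 4.2.2 lists "Intention to use a drop aid long term" as the third secondary outcome. The formal hypothesis in 12.1.4 is about the assigned population: "Patients assigned to a drop aid device will claim greater interest in long term use of the drop aid device", as against declining it. The testable form narrows this to two groups of respondents: "Mean patients claiming interest in long term use of the drop aid device compared to mean patient declining interest". The symbols follow suit. One mean is for those who claimed interest, and the other "is the mean patient who denied interest in long term use of the device".

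The data come from item 5 of the satisfaction survey in 15.2.4, "Would you use the drop aid long term". It has four answers: *Yes*, *No*, one for patients without a drop aid, and "I did not use the drop aid". The same form is used at the 3-week call and at the final visit (9.3.1, 9.3.2). Section 8 says these surveys are also how device compliance is judged.

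Section 10.4 lists "Failure to comply with drop aid instructions" among the reasons for which a subject will be withdrawn. Section 9.4 is permissive: "Subjects can also be withdrawn from the study if they demonstrate non-compliance for study procedures". The two sections need to be reconciled. Section 12.3 gives no denominator for this outcome, no rule for the non-use answer or for withdrawn patients, and no choice between the two surveys.

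**The concern.** Willingness to continue is being measured, and the patients least likely to be willing are also the likeliest to report non-use or to be withdrawn for not following the device instructions. If the two categories are applied as written, these patients are in neither. The result then describes those still using the device, while the hypothesis and the stated aim (likely use outside the study, 4.1 and 5) concern everyone given one. The expected direction favours the device. Because no rule is written down, the handling would be chosen after the answers are known. With ten patients per device, a few such cases move the percentage a long way.

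**Working it through.** **Inputs from the documents.** Ten patients per group (12.2) and four groups, three of them device groups (5). The plan's total reproduces: 4 × 10 = 40. Device patients: 3 × 10 = 30. For this outcome the plan gives no significance level, margin value, expected rate or dropout, so there is no further figure to reproduce.

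**Where each device patient falls in the 12.1.4 comparison.**

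| Final status | Category in 12.1.4 |
|---|---|
| Answers *Yes* | claimed |
| Answers *No* | denied |
| Answers that the device was not used | neither |
| Withdrawn before the final survey | neither, unless the 3-week answer is used |

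**Effect on the proportion.** Let N = 30 be assigned, Y the number of *Yes* answers, and k the number of the others in the last two rows.

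- Share among all assigned: Y/N.
- Share among yes/no answers: Y/(N − k), larger by the factor N/(N − k). For k = 3, 6 and 9 this is 1.11, 1.25 and 1.43.

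Y and k are assumptions. The p-values are exact one-sided binomial tails, P(X ≥ Y) with n = N − k and probability 0.5. They are only a yardstick, since the plan names neither this test nor a level.

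| k | N − k | Share, Y = 15 | p | Share, Y = 18 | p |
|---|---|---|---|---|---|
| 0 | 30 | 50.0% | 0.572 | 60.0% | 0.181 |
| 3 | 27 | 55.6% | 0.351 | 66.7% | 0.061 |
| 6 | 24 | 62.5% | 0.154 | 75.0% | 0.011 |
| 9 | 21 | 71.4% | 0.039 | 85.7% | 0.0007 |

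The number of *Yes* answers is constant down each column, so only the denominator changes.

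**Single device** (N = 10, Y = 5). Losing 1, 2, 3 or 4 of the others moves 50% to 5/9 = 55.6%, 5/8 = 62.5%, 5/7 = 71.4% or 5/6 = 83.3%.

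**Partial loss.** k counts only those who end up in neither category. If six patients give up the device but three of them tick *No*, the k = 3 row applies: 15/27 = 55.6%, not 62.5%.

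**The case against.** The strongest reply is that the plan never writes an exclusion. Section 12.1.4 states no denominator, and its hypotheses name the assigned population. That is true. A reader might infer that the protocol has decided to drop refusers; it has not. But the two defined terms leave non-users and withdrawn patients without a place, and 12.3 does not supply one.

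A reader might also infer that everyone who abandons a device is lost. The documents do not support that. The non-use answer most naturally describes someone who never used the device, and a patient who tried it and stopped can tick *No*. Item 5 is also asked at 3 weeks, so a patient withdrawn later may already have answered. Withdrawal under 9.4 is discretionary. Failing to follow instructions can mean incorrect use rather than refusal, and 10.4 also withdraws patients for a change of drop regimen. These points reduce the loss but do not remove it.

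A third tempting reading is that the trial's conclusion would reverse. Counts can be chosen that do this: 12 *Yes* and 9 *No* with nine lost gives 12/21 = 57% against 12/30 = 40%. Those counts are assumed, and only a raw majority changes (exact one-sided p = 0.33 for 12/21). With 15 or more *Yes* answers out of 30, no such reversal to a minority is possible.

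Finally, item 1 has the same non-use answer, so a reader might extend the point to patient satisfaction. Section 12.1.3 compares device with control patients, and on item 1 controls can only say that they have no drop aid. Changing the denominator does not address that comparison.

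**Conclusion.** The point holds in a limited form. As worded, 12.1.4 has no category for device patients who report non-use, or who are withdrawn for device non-compliance without a final survey, although its hypothesis covers all patients assigned to a device. The expected bias is towards greater apparent interest. Its size cannot be derived from the documents. On the assumption of 15 *Yes* among 30, losing 3 to 9 of the others raises the share from 50% to between 56% and 71%. This rests on ten patients per group being enrolled and on the lost patients not being ones who would have said *Yes*; the bias is smaller to the extent that some would have. It affects a secondary outcome, not the pressure comparison. It should be corrected because the better definition costs almost nothing.

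**What to change.** In 12.1.4 and 12.3:

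- Define the outcome as the proportion answering *Yes* to item 5 at the final visit among all patients assigned to a device (planned 30, and 10 per device).
- Count as not *Yes*: an answer of *No*, the non-use answer, and withdrawal for device non-use or a device-related event.
- Treat answers missing for other reasons, such as a regimen change or a missed survey, as missing. Add sensitivity analyses that use the 3-week answer and the best and worst cases. For example (assumed counts), with 15 *Yes* and two such patients, the main result is 15/28 = 53.6%, with bounds of 15/30 = 50.0% and 17/30 = 56.7%.
- Report the yes/no split among users as supplementary and label it as such.
- If item 1 is described within the device groups, use the same all-assigned denominator. Do not present this as a repair of 12.1.3.

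The cost is a short paragraph of text. No new survey question or visit is needed, but the reason for each withdrawal must be recorded well enough to separate non-use from other causes. No withdrawal rule changes. Counting the non-use answer as not *Yes* is a convention, and the stated proportion may be less favourable to the devices.
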